Training HIV providers to manage opioid dependence with buprenorphine/naloxone (BUP/NX) during HIV clinic visits has the potential to expand access to opioid dependence treatment while increasing engagement in HIV care. Buprenorphine/naloxone (BUP/NX), a partial opioid agonist recently available in Vietnam, has few drug-drug interactions with HIV or TB treatment medications, low overdose risk, no requirement for daily observed dosing and avoids the administrative requirements of MMT, making it highly feasible for use in busy HIV clinics.²¹⁻²³ As in other countries, HIV providers in Vietnam's 320 HIV clinics are well-positioned to adopt new treatments and successfully manage both HIV and opioid dependence as two interrelated chronic, but treatable illnesses. Studies of BUP/NX in HIV care settings are limited, however. Two U.S. pilot studies of BUP/NX suggest it is safe and feasible and reduces opioid use in HIV care, but were limited by lack of a comparison group²¹⁻²², and small sample size.²⁴ In both studies, the majority of participants were already on ART with high baseline rates of viral suppression, limiting the capacity to assess the effect of BUP/NX on HIV outcomes. Assessing the effectiveness of clinic-based BUP/NX with a high proportion of participants new to care, as we propose, provides the opportunity for assessing its ability to close gaps in the HIV care cascade in real-world HIV clinic settings.

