The primary objective of this proposal is to add to the palette of treatment options by comparing the effect of two opioid dependence treatment delivery models on improving the HIV care engagement and outcomes in Vietnam. We propose a multisite, open-label, randomized, flexible-dose noninferiority trial of buprenorphine/naloxone (BUP/NX) (n=225) versus methadone maintenance therapy (MMT) referral (n=225) for treatment of opioid dependence in HIV-infected participants in 6 Vietnam HIV clinic research sites. The study is conducted in partnership with colleagues at Hanoi Medical University (HMU), the Provincial AIDS Control (PAC) authorities of Hanoi, Thanh Hoa, and Bac Giang, the Vietnam National Institute of Mental Health, and Oregon Health & Science University.

Study sites are 4 HIV clinics in Hanoi, 1 in Thanh Hoa, and 1 in Bac Giang; epicenters of Vietnam's HIV and heroin epidemics, all of which are associated with MMT and HIV testing and counseling centers. A research coordinating center at HMU provides additional outreach, recruitment, non-medication-related study procedures and links participants to participating HIV clinic sites for clinical management. HIV providers will be trained to manage opioid dependence using BUP/NX.

Participants are HIV-infected participants with opioid dependence new to HIV care, recruited from HIV clinics, MMTs, and associated HIV testing centers. Participants randomized to BUP/NX will receive BUP/NX after successful completion of medication induction and stabilization. Participants randomized to BUP/NX will receive a taper after 12 months of study drug exposure, with referral for MMT. Participants randomized to MMT will receive usual care, which is case-manager-assisted referral to MMT. All participants receive clinic-based individual counseling and HIV care.

The primary outcome of HIV-1 viral load will be measured at baseline, 6, and 12 months. Secondary outcomes, including self-reported drug use, urine drug screens (UDS), and measures of HIV care engagement (adherence, retention) will be assessed quarterly through 12 months follow-up. Qualitative interviews with participants, family members of participants, and providers in years 1 through 4 will identify lessons-learned for scale-up of HIV clinic-based BUP/NX.

Figure 2. Study Schema

There are three specific aims in this protocol:

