research coordinating center at HMU provides additional outreach, recruitment, non-medication-related study procedures and links participants to participating HIV clinic sites for clinical management. HIV clinics were selected based on the prevalence of untreated active opioid dependence among new participants with a history of IDU, ability to enroll at least 120 participants over the course of the study, availability of methadone maintenance, and support of local authorities. Medical directors at participating sites estimate that < 5% of participants with active heroin use currently access MMT. All HIV clinic sites have on-site counseling, case management, phlebotomists and pharmacy services on-site, and are affiliated with Voluntary Counseling and HIV Testing (VCT) services and MMT programs in their surrounding communities that have capacity for accepting new MMT referrals.

Study Design and Procedures

450 Participants (225 BUP/NX and 225 MMT) HIV-infected participants with active opioid dependence will be enrolled in the study across participating sites. Outreach activities will seek to identify patients new to HIV care or registered for care at participating HIV clinics but not on ART, though participants are not required to be ART treatment-naïve. Participants will be enrolled in the study for approximately 12 months, with 6 research visits total.

Inclusion Criteria:

- HIV positive
- Have a current moderate to severe DSM-5 opioid use disorder
- Urine drug screen positive for opioids
- Interested in receiving treatment for opioid dependence
- Are age 18 or greater
- Are willing to practice effective method of birth control, if female

Exclusion Criteria:

- Have a known hypersensitivity to buprenorphine or naloxone
- Have an AST & ALT > 5x upper limit
- Are currently pregnant or breastfeeding
- Have a serious medical or psychiatric illness in past 30 days (e.g. opportunistic infection, psychosis) that precludes safe participation in the opinion of study physician
- Have received methadone maintenance treatment within 30 days of consent

Known vulnerable populations will be excluded from participation; this includes children, pregnant women, decisionally-impaired adults, and prisoners.

Prisoners:

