Those who participate in pilot testing receive a one-time amount of 100,000^d. Those who participate in the qualitative interviews will receive 200,000^d for each interview.

Travel reimbursement will be provided for research visits only (not medication induction or other medication dispensing visits) at the rate of 3,000^d per kilometer.

Participants will not pay for the following research-associated laboratory testing:

- Screening: CBC, AST/ALT, CD4
- Baseline: Hepatitis B, Hepatitis C, tuberculosis screening (PPD test), HIV viral load, HIV confirmatory testing when only rapid test results available, HIV genotype resistance for participants on ART and who have viral loads > 200.
- 6 Month: CD4 and HIV viral load
- 12 Month: CD4, HIV viral load, HIV genotype resistance for participants on ART and who have viral loads > 200

Referral Compensation

- Participants can refer individuals to the study, and upon successful completion of randomization, receive 100,000^d.
- Community outreach groups (peer educators, self-help, etc) can refer individuals to the study, and upon successful completion of randomization, receive 300,000^d. Outreach workers will receive 50,000 for each person pre-screened, regardless of randomization.

Insurance Payments

Beginning January 1st, 2017, the government of Vietnam is requiring health insurance for HIV-infected patients. For those unable to obtain other insurance, the study will pay for insurance premiums while they are enrolled in the study. This will be coordinated with Hanoi Medical University and Hanoi PAC (Provincial AIDS Center) and payments will be directly made to the insurance companies, not to participants. Currently, this is expected to cost about 680,000 VND (\$30 US dollars) per year but could be change per national or local policy. Without the study paying for insurance, some participants would likely become ineligible to receive antiretroviral therapy, thus biasing the study's secondary outcomes as well as jeopardizing retention rates.

Randomization

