Adverse Events • Paper Log • eCRF • Serious Adverse Events eCRF								X
Protocol Deviation • Paper Log • eCRF								X

Table 2: Table of Assessments								
	Pre-Screening	Screening	Baseline	3 Month	6 Month	9 Month	12 Month	As Needed Only
Study Termination Form							X	X (if ppt ends early)
*chart abstraction possible								

Visit Procedures

Survey Data

Research assistants will administer participant surveys in a confidential setting using real-time, secure, web-based electronic data entry. All survey measures have been translated into Vietnamese and been field tested and adapted for cultural appropriateness and feasibility for electronic data collection in Vietnam during previous research.

Survey data measurements include:

- Demographics
- Drug and alcohol use
- Addiction treatment
- HIV treatment
- Co-morbid conditions including physical and mental health
- Quality of life

Medical Chart Data

Research assistants will review participant HIV clinic and MMT medical charts quarterly to inform outcome measures including receipt of ART, retention in care, and adherence to study treatment condition (buprenorphine, methadone dosing, counseling visits). Medical charts will be reviewed at Baseline to establish diagnoses of Hepatitis B, Hepatitis C, and Tuberculosis. If not available in medical chart, research staff will obtain testing as necessary.

Biologic Data

Urine samples for pregnancy and urine drug screens (morphine, methamphetamine, methadone, amphetamine, buprenorphine) will be collected and processed in the HIV clinic using point of care testing.

Viral load specimens will be drawn at baseline, 6, and 12 months, and processed for transport at HIV clinic, then transported to the National Hospital for Tropical Disease for centralized lab testing. HIV viral load testing (the primary outcome) is performed with Real-time RT-PCR on Real-time ABI 7500 machine with reagents and primers made by Invitrogen.¹¹⁰ The current viral load technique is certified for a lower limit of HIV-1 RNA detection of 55 copies/mL.

All other phlebotomy measurements (Safety Labs, and CD4) will be either drawn at the appropriate times following the above schedule or will be chart-abstracted as required. They will be drawn and processed for analysis at the HIV clinic locally.

Study physicians will conduct baseline physical exams to assess for medical appropriateness for participation.

Qualitative Data

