Participants may benefit from participation in the proposed study by engaging in treatment for both HIV and opioid dependence. Both buprenorphine and methadone have a strong history of improving opioid dependence outcomes across many studies, worldwide. Individual findings may be helpful in participants' clinical care if they wish the data to be shared with their clinicians. Involvement in the study may positively affect the chances of abstinence.

Data Analysis

Aim 1: Assess the effect of clinic-based BUP/NX (n=225) versus MMT referral (n=225) on HIV treatment engagement and outcomes in HIV-infected participants with opioid dependence.

- **H1a:** Participants randomized to BUP/NX will have noninferior rates of HIV viral suppression (HIV-1 RNA < 200 copies/mL) on 12 month blood draw compared with MMT referral.
- **H1b:** Participants randomized to BUP/NX will have greater ART initiation, adherence, and retention in HIV care at 12 months versus MMT referral.

Overview. Aim 1 assesses the effect of clinic-based BUP/NX on HIV treatment engagement and outcomes using the study procedures outlined in the Study Design and Procedures section.

Dependent variables: The primary outcome for Aim 1 is HIV viral suppression at 12 months (lab data, binary). HIV viral suppression is defined as an HIV-1 RNA PCR test < 200 copies/mL, using the ultra-sensitive HIV real-time PCR assay available at the NHTD laboratory, consistent with current U.S. Guidelines for the Use of Antiretroviral Agents in HIV-1-Infected Adults and Adolescents.³⁵ The rationale for this definition is to avoid the influence of “blips” in HIV RNA viral load which commonly occur at levels between 20 and 200 copies/mL using current PCR assays and which are of limited clinical significance¹³²⁻¹³³. Secondary outcomes for Aim 1 include ART initiation at 12 months (binary, chart review); 100% ART adherence at 12 months (binary, self-report), and retention in HIV care at 12 months (binary, chart review).

Potential Covariates: We will consider participant demographics, alcohol and other drug use, HIV history, comorbid conditions, attitudes toward treatment services, and social support characteristics as potential covariates.

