The primary analysis for this study will be a mixed logistic regression model comparing BUP/NX versus MMT on viral suppression rates over time. Treatment comparisons will be performed under the Intent-to-Treat (ITT) criterion; participants will be analyzed in the arm to which they

were randomized regardless of subsequent events. In this mixed logistic model, each (binary) outcome serves as a dependent variable; treatment effect (BUP/NX versus MMT referral) and time effect (e.g., baseline, 6, and 12 months) will be considered main effects. An interaction between these two main effects, e.g., treatment*time, will be included in the model. Model-fitted, marginal risk and RD estimates will be obtained at each time by applying an inverse-logit transformation to coefficients from the logistic regression model, with standard errors estimated via the delta method. We will test the primary hypothesis of noninferiority by comparing the lower bound of a 95% confidence interval to the prespecified margin (i.e., 13%); if the lower confidence limit of the RD is greater than -13%, we will conclude that the BUP/NX is noninferior to MMT. The model will include subject-level random intercepts in order to account for repeated measurements within individuals. Attrition is unavoidable in a longitudinal study; in our study, we anticipate an attrition rate of 20%. The mixed model approach is a recommended strategy for handling missing data in clinical trials under the assumption that the data are missing at random.

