Power Analysis: Since our primary outcome in this aim is opioid use, the power analysis is based on this outcome. With our proposed sample size (450 as the total, 225 for each treatment arm), we have gained the power of 91% to detect 15% in difference between the two groups at

the level of alpha 0.05, provided that the proportion of UDS positive for opioid at 12 months will be 65% for MMT referral. This power analysis is conservative due to not maximizing multiple-time-point data from our longitudinal study. We anticipate the power is much higher to off-set the complexity of the mixed logistic model (adjusting for some covariates) we propose in the data analysis plan (see below).

Data Analysis Plan: The primary (binary) outcome for Aim 2 is opioid use, collected at baseline, 3, 6, 9, and 12 months. We will use an approach as in Aim 1.

Aim 3: Assess BUP/NX implementation experience to inform national scale-up of clinic-based BUP/NX.

Overview. We will conduct qualitative interviews with HIV providers, administrators, and opioid dependent participants, and their family members in participating HIV clinics annually during years 1 through 4 to document and describe formative implementation strategies, challenges, and best practices. Results inform policy-making for national scale-up of clinic-based BUP/NX in Vietnam.

Qualitative Procedures and Analysis. The implementation aim documents the experience of providers and participants at clinics to further inform adoption of BUP/NX in Vietnam and guides planning efforts and policy-making. Data also monitor the performance of the sites and qualitative interviews provide critical detail for enhanced understanding of the findings from the trial (Aim 1 and 2). Using the Taxonomy of Mixed Method Designs¹³⁴⁻¹³⁶, our design has a QUAN +Qual structure with simultaneous data collection and emphasis/weight placed on the quantitative efforts. The qualitative data provide complementary information to illuminate and expand the findings from Aims 1 and 2.

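### The primary model leaves the 12-month risk difference essentially unadjusted for baseline viral suppression; the analysis is valid, and the only cost is a probably small loss of precision

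*Combined protocol and SAP*

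**What the plan says.** The Aim 1 Data Analysis Plan states that "treatment effect (BUP/NX versus MMT referral) and time effect (e.g., baseline, 6, and 12 months) will be considered main effects". It adds a treatment-by-time interaction and subject-level random intercepts, and tests noninferiority on the model-based marginal RD against -13 points. It does not constrain the arms to share a baseline level.

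The Potential Covariates paragraph is a candidate list: "We will consider participant demographics, alcohol and other drug use, HIV history, comorbid conditions" and further groups. Baseline viral load is not named, and no covariate set or selection rule is fixed. The Aim 2 Power Analysis refers to "the mixed logistic model (adjusting for some covariates) we propose in the data analysis plan", also without naming any. The Randomization section gives blocks of 10 and no stratification factor.

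Baseline viral load is collected. Biologic Data says "Viral load specimens will be drawn at baseline, 6, and 12 months", and Objectives says "The primary outcome of HIV-1 viral load will be measured at baseline, 6, and 12 months".

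Entry status can vary. The background section describes a trial "with a high proportion of participants new to care, as we propose", and Study Design and Procedures directs outreach to people new to HIV care or not on ART, "though participants are not required to be ART" treatment-naïve. The list of tests at no charge includes, at baseline, "HIV genotype resistance for participants on ART and who have viral loads > 200", so some participants are expected to be on ART at entry.

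**The concern.** A model that contains the baseline measurement looks as if it adjusts for it. With a treatment main effect and a treatment-by-time interaction, it does not. The six arm-by-time means are free, so a chance difference between arms at baseline is absorbed by the baseline terms and leaves the 12-month contrast almost untouched.

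Baseline suppression could predict 12-month suppression in those who enter on ART. Omitting it would make the interval for the RD wider than it need be, in a trial whose noninferiority power on its own reference inputs is about 69%. The candidate list does not close the gap, because a covariate that will only be considered is not pre-specified.

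**Working it through.** **The plan's own figure.** The superiority calculation, kept for reference, uses 50% v 65%, 80% power and alpha .05 (taken as two-sided). The pooled-variance formula, with mean rate 0.575, gives

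n = [1.96 × √(2 × 0.575 × 0.425) + 0.842 × √(0.25 + 0.2275)]² / 0.15² = 169.3, so 170 per arm and 340 in total, as stated.

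With 20% loss, 450 × 0.8 = 360, or 180 evaluable per arm.

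**Does the planned model adjust for baseline?** This was simulated with 225 per arm, equal arms, a random-intercept logistic model and 250 trials per setting. Assumed suppression was 35% at baseline and 50% at months 6 and 12. The baseline-to-12-month correlation was about 0.28, 0.45 or 0.59.

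- Complete data: the planned model's marginal RD had correlation 0.9999, 0.999 and 0.996 with the raw 12-month difference. Its slope on chance baseline imbalance was 0.27, 0.46 and 0.65. A baseline-adjusted estimate had slopes from -0.03 to 0.04.
- With 20% of 12-month values missing, the random intercept draws on earlier values (correlation with the raw difference 0.96-0.99), but imbalance still carries through (slopes 0.34, 0.49, 0.67).
- All estimators had a mean RD of about zero, so there is no bias.

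**Size of the loss.** From the plan: 50% suppressed (its MMT rate, applied here to both arms), 180 per arm, margin 0.13, 95% CI. Assumed, because the documents give neither: the share suppressed at entry (p0) and the share of those still suppressed at month 12 (s).

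- φ = (s − p) × √[p0 / (1 − p0)] / √[p(1 − p)]
- SE = √[2p(1 − p)/180 × (1 − φ²)]
- Power = Φ(0.13/SE − 1.96)

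Unadjusted: SE = √(0.5/180) = 0.0527, half-width 10.33 points, power = Φ(0.507) = 69.4%.

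| p0 | φ (s = 80%, 90%) | Half-width, points | Power gain, points |
|---|---|---|---|
| 2% | 0.09, 0.11 | 10.29, 10.26 | 0.3, 0.6 |
| 5% | 0.14, 0.18 | 10.23, 10.15 | 0.8, 1.5 |
| 10% | 0.20, 0.27 | 10.12, 9.96 | 1.8, 3.2 |
| 20% | 0.30, 0.40 | 9.85, 9.47 | 4.0, 7.4 |

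At p0 = 10% the gain equals having 180/0.96 = 187.5 to 180/0.929 = 193.8 evaluable per arm. If 12-month suppression is 80%, unadjusted power is 86.9% and the gain is 0.0-0.2 points at p0 of 5-10%.

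**Simulation of both models.** 10,000 trials per setting, 180 per arm, complete data, assumed 6-to-12-month correlation 0.7, with a weak penalty (normal prior, SD 10) on the baseline coefficients of the covariate model. Power, as planned v with the covariate:

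- p0 5%: 68.8 v 70.1% (s = 80%) and 69.5 v 71.4% (s = 90%)
- p0 10%: 68.6 v 70.7% and 69.7 v 73.5%
- p0 20%, s = 90%: 69.2 v 77.1%

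False noninferiority at a true RD of -13 points was 2.3-2.8% as planned and 2.2-2.8% with the covariate (nominal 2.5%). With 225 per arm, p0 10% and 20% missing at month 12 completely at random, power was 70.4 v 73.5% and 70.5 v 74.6%; false noninferiority was 2.3-2.4% v 2.5-2.7%.

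**Sparse cells.** With p0 5% and s 90%, the chance that nobody suppressed at entry is unsuppressed at month 12 is (1 − 0.05 × 0.1)^360 = 16.5%. With p0 2% it is 0.998^360, about 49%. An unpenalised 12-month baseline coefficient may then have no finite estimate, although the RD can still be estimated.

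**The case against.** The strongest reply is that nothing here is an error. A longitudinal model with baseline as a time level is legitimate, and its error rate is as nominal. The gain rests wholly on assumed inputs, and recruitment of people new to care or not on ART points to 5% or fewer entering suppressed, where the gain is about 1.5 points at most. The 69% is built on the 50% rate from the superseded superiority calculation, and one or two points do not repair it. The remedy is also least stable where few enter suppressed. All of this stands, and it is why the point is graded low.

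It does not remove the point. The covariate is already collected, and the change keeps the RD, the margin and the intention-to-treat comparison. HIV history might be read to include viral load, but it is only to be considered.

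Two stronger readings are tempting. A reader might infer that the primary result is biased or the test invalid; randomisation and the simulated error rates say otherwise. A reader might also see a conflict in Aim 2, where the Overview lists months 3 to 12 and the Data Analysis Plan adds baseline. The first lists assessments after randomisation and the second lists collection times. They are compatible, and the 12-month RD is essentially unaffected.

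**Conclusion.** The point holds as a low-severity matter of precision. The planned 12-month RD is valid but essentially unadjusted for baseline suppression. Validity here assumes data missing at random and an RD that is truly marginal, that is, averaged over the random intercept.

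The likely gain from adjustment is between a fraction of a point and about 3 power points. It reaches 4.0-7.4 points only if about 20% enter suppressed, which the recruitment plan does not suggest, and it is close to zero if 12-month suppression is near 80%. The entry rate and its correlation with month 12 are assumptions throughout.

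**What to change.** In the Aim 1 Data Analysis Plan:

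- Model months 6 and 12 as outcomes, with baseline suppression (<200 copies/mL) and its interaction with time as named, pre-specified covariates.
- Report a marginal 12-month RD standardised over the baseline distribution of all randomised participants, including those with a baseline but no follow-up viral load.
- Give a rule for a missing baseline viral load, for example a single imputation blind to arm or a missing-value indicator, so that nobody is dropped.
- Include baseline suppression in the planned multiple imputation.
- Fix a sparse-cell rule in advance, with its trigger and size, for example a normal prior with SD 10 on the baseline coefficients.

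Constraining the arms to a common baseline is an alternative only if its SE is checked. With 5-10% suppressed at entry and the assumed 0.7 correlation between months 6 and 12, that model's mean SE was 0.0480-0.0512 against a true SD of 0.0507-0.0539, and false noninferiority was 2.8-3.4%. One random-intercept variance may understate the SE when the 6-to-12-month correlation is much stronger than the baseline-to-12-month one.

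The cost is SAP text and a slightly more complex model, for a gain that may be small. No new data are needed.

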Power Analysis: This study was initially conceived and powered as a superiority trial. Based on a desire to augment the existing treatment options rather than justify a preferred pharmacotherapy, the design was revised with approval from the study sponsor (see attached approval letter from sponsor). For reference, the original power analysis is below:

Sample size calculations are based on the Aim 1 primary outcome of HIV viral suppression (HIV-1 RNA < 200 copies/mL). We estimate that 340 participants will be required (170 BUP/NX, 170 MMT) to detect a 15% difference in HIV viral suppression between the two study conditions at 12 months, assuming 80% power, alpha of .05, and a viral suppression of 50% in the referral for MMT group. We increase the sample size to 450 participants (225 BUP/NX, 225 MMT) to conservatively account for potential loss to follow-up of 20%. This sample size calculation is additionally conservative in that it does not account for multiple-time-point data that will be available from our longitudinal study. We favor a conservative estimate to off-set the complexity of our proposed mixed logistic model in the data analysis.

Noninferiority Margin: For the primary outcome of viral suppression, we pre-specified a non-inferiority margin of $\leq 13\%$ in the risk difference (RD) comparing BUP to MMT. The noninferiority margin was selected based on margins ranging from 10% to 15% for noninferiority trials testing the effect of antiretrovirals on HIV viral suppression. After choosing the 13% margin, we conducted an informal survey of national HIV-addiction treatment experts who confirmed that it was clinically relevant and appropriate

Data Analysis Plan: Univariate statistics will be used to describe participant characteristics and study outcomes using mean/SD for continuous variables and percentages for categorical variables. Independent samples T-tests will be used to test bivariate differences between the main independent variable (clinic-based BUP/NX versus MMT referral assignment) and baseline continuous variable participant characteristics (e.g., age, CD4 nadir, etc.). Chi-square/Fisher-Exact test will be performed to assess differences between the main independent variable and categorical variables.

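### The primary risk difference is called marginal, but taking the inverse-logit of random-intercept coefficients does not give the difference in arm rates to which the 13% margin applies

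*Combined protocol and SAP*

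**What the plan says.** The hypothesis (H1a) is about arm-level rates at 12 months: BUP/NX is to show "noninferior rates of HIV viral suppression (HIV-1 RNA < 200 copies/mL) on 12 month blood draw compared with MMT referral". The Noninferiority Margin paragraph sets 13% "in the risk difference (RD) comparing BUP to MMT".

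The Aim 1 Data Analysis Plan specifies a mixed logistic model with treatment, time (baseline, 6 and 12 months) and their interaction. On within-person correlation it says: "The model will include subject-level random intercepts in order to account for repeated measurements within individuals". On the effect measure it says that "marginal risk and RD estimates will be obtained at each time by applying an inverse-logit transformation to coefficients from the logistic regression model", with delta-method standard errors. The decision rule is: "if the lower confidence limit of the RD is greater than -13%, we will conclude that the BUP/NX is noninferior to MMT". The mixed model is also the plan's answer to attrition, as a "recommended strategy for handling missing data in clinical trials under the assumption that the data are missing at random".

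The sensitivity analyses change how missing data are handled or which participants are analysed. They describe no other way of obtaining the risk difference, and no software is named.

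**The concern.** In a random-intercept logistic model, the inverse-logit of the summed fixed effects is the suppression probability of someone whose random intercept is exactly zero. It equals the arm's average probability only if the intercept SD is 0 or the arm's rate is exactly 50%. Otherwise the average is pulled towards 50%.

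So the sentence names one quantity (marginal) and describes the calculation of another. An analyst who follows it literally compares the lower limit of an intercept-zero contrast with a margin that was chosen for a difference in rates. Two competent analysts could report different lower limits from the same fitted model, and the noninferiority conclusion depends on that limit.

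**Working it through.** **Inputs from the plan.** 225 per arm; 20% attrition, so 225 × 0.8 = 180 per arm at month 12; margin 13 points; lower limit of a 95% CI; "a viral suppression of 50% in the referral for MMT group"; and a design "to detect a 15% difference in HIV viral suppression between the two study conditions at 12 months", which implies 50 + 15 = 65% in the other arm.

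**Inputs not in the plan (assumed).** Random-intercept SD of 0.5, 1, 2 and 3, corresponding to within-person correlations of 0.06, 0.17, 0.39 and 0.54 at a 50% rate. MMT rates of 65, 80 and 90% are added scenarios; in the plan's calculation 65% belongs to BUP/NX, not MMT.

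**The plan's own figure.** For 50% vs 65%, two-sided alpha 0.05 and 80% power:

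n = [1.96·√(2 × 0.575 × 0.425) + 0.842·√(0.25 + 0.2275)]² / 0.15² = 169.3, rounded up to 170 per arm (340 in total).

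The plan's figure is reproduced, and 340/0.8 = 425 is below 450. This calculation does not use the disputed step.

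**Step 1: the two quantities.** With linear predictor η and intercept b ~ N(0, SD²):

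- arm rate = average of expit(η + b) over b
- calculation as written = expit(η)

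Example at SD 2: an MMT rate of 50% has η = 0, so expit(η) = 50.0%. A BUP/NX rate of 37% needs a predictor for which expit(η) = 29.4%. The true difference is 37 - 50 = -13.0 points; the calculation as written gives 29.4 - 50.0 = -20.6. In reverse, a reading of -13 as written is a true difference of only -8.0.

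| MMT rate | Quantity (points) | SD 0.5 | SD 1 | SD 2 | SD 3 |
|---|---|---|---|---|---|
| 50% | True -13 reads as | -13.7 | -15.5 | -20.6 | -26.0 |
| 50% | Effective margin | -12.3 | -10.8 | -8.0 | -6.1 |
| 65% | True -13 reads as | -13.7 | -15.4 | -20.1 | -24.9 |
| 65% | Effective margin | -12.4 | -11.0 | -8.6 | -7.3 |
| 90% (hypothetical) | True -13 reads as | -12.7 | -12.0 | -9.2 | -6.0 |

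The direction reverses at an MMT rate of about 85, 85, 82 and 80% for the four SDs.

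**Step 2: effect on the decision.** Simulated trials used 225 per arm, an assumed 30% baseline suppression, month-6 rates equal to month-12 rates, and 10% and 20% missing completely at random at months 6 and 12. The plan's model was fitted by maximum likelihood with delta-method intervals; 1,500 trials per cell. Entries are the percentage declaring noninferiority, as written / averaged.

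| Truth | SD 0.5 | SD 1 | SD 2 | SD 3 |
|---|---|---|---|---|
| 50% vs 50% | 65 / 70 | 55 / 70 | 33 / 71 | 22 / 73 |
| 65% vs 65% | 70 / 74 | 62 / 74 | 49 / 75 | 42 / 75 |
| 50% vs 37% | 1.7 / 2.4 | 0.8 / 1.9 | 0.4 / 2.5 | 0.1 / 2.0 |
| 65% vs 52% | 2.3 / 2.6 | 0.7 / 2.1 | 0.1 / 3.1 | 0.0 / 2.9 |
| 80% vs 67% | 2.5 / 2.7 | 1.3 / 2.3 | 1.7 / 2.1 | 5.4 / 2.3 |

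The last three rows have a true difference of -13, where the nominal rate is 2.5%. Monte Carlo error is about 0.4 points at 2.5% and 1.3 points at 50%.

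**Step 3: hand check at 50% vs 50%.** SE = √(2 × 0.25/180) = 5.27 points. With the full margin, Φ(13/5.27 - 1.96) = 69%. With the effective margins 12.3, 10.8, 8.0 and 6.1, the same formula gives 65, 54, 33 and 21%, close to the simulated 65, 55, 33 and 22%. The power loss is what the shrunken margin implies.

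**The case against.** The strongest reply is that the plan names the right target. The sentence is already compressed: it does not spell out forming a linear predictor for each arm and visit, so the averaging step may also be unwritten rather than excluded. That is possible, and in that case only wording is at fault. But no section supplies the step, and a primary decision rule should be executable from its text.

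Second, near the plan's own rate the literal rule does not pass an inferior arm; false noninferiority stays below 2.5%. This stands. The harm there is lost power and an undeclared tighter margin. Nor is power loss universal: a separate simulation (180 per arm, other visit-rate assumptions) gave 92.5% as written against 84.8% averaged at equal 80% rates and SD 2.

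Third, the size rests on an SD that the plan does not give. This also stands. At SD 0.5 the risk difference is off by less than 1 point and power falls by 4 to 5 points. The 50% rate comes from the superseded superiority calculation, and the assumed baseline and month-6 rates have no source in the plan. The Step 1 results do not depend on those two assumptions, but the simulated percentages may.

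**Conclusion.** The concern holds: the calculation as written does not produce the quantity that H1a and the margin refer to. Whether the trial would report a wrong number depends on whether the analyst follows the literal text.

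If so, the rule is conservative at MMT rates of 50% and 65%, with an effect ranging from minor at SD 0.5 to severe at SD 2 or 3. Near 80% it is nominal to slightly conservative for SDs up to 2. Above about 80 to 85%, which the plan does not project, it is anti-conservative: in the separate simulation at 90% vs 77% and SD 2, noninferiority was declared in 28.5% of trials as written against 3.3% with averaged risks. The calculation therefore cannot be defended as always safe.

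**What to change.** State in the Aim 1 Data Analysis Plan that the 12-month arm risks and their difference are obtained by averaging the inverse-logit over the estimated random-intercept distribution of the fitted model, with a delta-method or bootstrap standard error that includes the variance parameter. Apply the -13% rule to that difference.

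This keeps the model and its missing-at-random argument. Unweighted GEE is not an interchangeable substitute. In a check where month-12 dropout in the BUP/NX arm depended on observed month-6 status, with equal true 50% rates, it was biased by +0.1, +1.1, +2.5 and +3.7 points for the four SDs, while the averaged difference stayed within 0.2 points of zero. With 20% attrition, a GEE approach would need weighting or multiple imputation.

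Use the same calculation for any risks or differences reported for the secondary and Aim 2 outcomes; their superiority tests of no difference are unaffected.

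The cost is one or two sentences and a different post-estimation step, with no new data and no change of model. If averaging was always intended, only the wording changes.
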